Written and verbal informed consent will be obtained from all participants prior to treatment (Appendix 1). An electronic questionnaire including the Numerical Rating Scale (NRS) and analgesic intake will be sent to patients (Appendix 2). Patients will be contacted by phone and asked to complete the questionnaire online. Submitted responses will not be editable. The primary outcome will be postoperative pain, while secondary outcomes will include analgesic consumption and flare-up incidence.

Inclusion Criteria

- Asymptomatic teeth with delayed positive response to thermal and electric pulp testing
- Vital teeth with signs of irreversible pulpitis
- Mature mandibular first or second premolars
- Periodontally healthy teeth

Exclusion Criteria

- Patients with systemic conditions (e.g., diabetes, immunocompromised status, pregnancy)
- Antibiotic use within the past month
- Use of analgesics within 7 days prior to treatment
- Known allergy to materials used
- Teeth with periapical lesions
- Non-vital or symptomatic teeth
- Teeth requiring post-core restorations
- Calcified canals, root resorption, or immature teeth

Randomization and Blinding

Participants will be randomly assigned to one of four groups using a computer-generated randomization sequence. Allocation concealment will be ensured using sealed opaque envelopes.

Patients and outcome assessors will be blinded to group allocation. Due to the nature of the intervention, the operator could not be blinded.

A total of 180 sealed envelopes containing combinations of TruNatomy or ProTaper Gold systems and AH Plus or TotalFill BC sealers will be prepared and mixed in an opaque container. Each patient will select one envelope, which determines the assigned group. To minimize bias, the operator will open the envelope only after gaining access to the root canal.

Treatment Protocol

All procedures will be performed by a single experienced clinician in a standardized clinical setting, using the same irrigation solutions and obturation techniques, and completed in a single visit.

Inferior alveolar nerve block anesthesia will be administered using 2% articaine hydrochloride with 1:80,000 epinephrine (Jetokain; Adeka). After rubber dam isolation, caries and old restorations will be removed, and standard access cavities will be prepared.

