Working length will be determined using an electronic apex locator (Raypex 6; VDW) and confirmed radiographically. Glide path preparation will be performed using size 8–10 K-files, and apical patency will be confirmed with a size 10 K-file.

Root Canal Shaping

- **TruNatomy Groups (Groups 1–2):**
Preparation will be performed at 500 rpm and 1.5 Ncm torque using TruNatomy Glider (17/0.02) followed by Prime file (26/0.04).
- **ProTaper Gold Groups (Groups 3–4):**
Preparation will be performed at 300 rpm and 2 Ncm torque using ProGlider followed by SX, S1, S2, F1, and F2 files.

Irrigation with 2.5% NaOCl will be performed using a 30-gauge side-vented needle. Final irrigation will include activated NaOCl (EndoActivator), EDTA, distilled water, and 2% chlorhexidine.

Obturation

Modified single-cone technique will be used:

- Group 1: TruNatomy + AH Plus
- Group 2: TruNatomy + TotalFill BC
- Group 3: ProTaper Gold + AH Plus
- Group 4: ProTaper Gold + TotalFill BC

Excess gutta-percha will be removed and compacted below CEJ, followed by composite restoration (Filtek Z250; 3M ESPE).

Postoperative Pain Assessment

Primary Outcome

Postoperative pain will be evaluated at different time points—6, 12, 24, 48, and 72 hours, as well as on the 7th day—using the Numerical Rating Scale (NRS). The NRS is a numerical version of the Visual Analog Scale (VAS), ranging from 0 (no pain) to 10 (unbearable pain) (8, 9). It will be explained to participants as follows:

- No pain (0)
- Mild pain (1–3): Low-level pain that does not require analgesics
- Moderate pain (4–6): Tolerable pain that can be controlled with analgesics\
- Severe pain (7–10): Unbearable pain that is not adequately controlled by analgesics and often requires rest

Postoperative Analgesic Protocol: All patients will be prescribed 400 mg ibuprofen and will be advised to use it only in cases of severe pain. Analgesic intake will be recorded.

Follow-up Visits: Follow-up visits will be scheduled on the 7th day to clinically confirm patient-reported outcomes.

Statistical Analysis

Data will be analyzed using appropriate statistical software. Statistical significance will be set at $p < 0.05$.

References

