Appendix 2. Patient Pain Diary Form

Study Title: Impact of Trunatomy and Protaper Gold Ni-Ti Systems Using Resin-Based or Bioceramic Sealers on Postoperative Pain After Root Canal Treatment: A Randomized Clinical Trial

Participant ID: _____

Date of Treatment: _____

Tooth Number: _____

Instructions to the Patient

After your root canal treatment, please record the level of pain you experience at the following time intervals. Use the Numerical Rating Scale (NRS) below to indicate the intensity of your pain:

Pain Score	Description
0	No pain
1–3	Mild pain
4–6	Moderate pain
7–10	Severe pain

Numerical Rating Scale (NRS): 0 1 2 3 4 5 6 7 8 9 10
(0 = No Pain 10 = Worst Possible Pain)

Pain Record Table

Time After Treatment	Date / Time Recorded	Pain Score (0–10)	Notes (e.g., pain type, analgesic taken, other symptoms)
6 hours			
12 hours			
24 hours			
48 hours			
72 hours			
7th day			

Analgesic Use (if any):

Medication Name	Dose	Time Taken	Reason (if other than pain)

Patient Signature: _____ Date: _____

Investigator Signature: _____ Date: _____

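### The NRS explanation describes severe pain (7–10) partly by analgesic failure, although ibuprofen is advised only for severe pain, and its top anchor differs from the diary's

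*Protocol*

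**What the plan says.** Three parts of the Protocol bear on this point.

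- **Postoperative Pain Assessment, Primary Outcome.** The NRS is introduced as "ranging from 0 (no pain) to 10 (unbearable pain"). The band descriptions that follow are meant for patients: "It will be explained to participants as follows". The top band is worded as "Severe pain (7–10): Unbearable pain that is not adequately controlled by analgesics and often requires rest". The band just below it is worded as "Moderate pain (4–6): Tolerable pain that can be controlled with analgesics".
- **Postoperative Analgesic Protocol.** The advice on rescue medication comes straight after the scale and reads "All patients will be prescribed 400 mg ibuprofen and will be advised to use it only in cases of severe pain".
- **Appendix 2, Patient Pain Diary Form.** The instruction is "Use the Numerical Rating Scale (NRS) below to indicate the intensity of your pain". The bands have the same four labels and the same cut-points, with no reference to analgesics. The anchors read "0 = No Pain 10 = Worst Possible Pain".

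Pain on the NRS is the primary outcome. The Patient Selection section adds that "secondary outcomes will include analgesic consumption and flare-up incidence".

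**The concern.** An NRS score should record how strong the pain is. The verbal explanation brings in a second property, whether analgesics control the pain, and uses it to separate moderate from severe. The analgesic advice then makes severity the condition for taking ibuprofen. Severity is thus described partly by response to a drug, and use of that drug depends on severity.

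The wording for the top of the scale is also not the same in the explanation and on the form.

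What is at stake is the meaning of the higher scores on the primary outcome, and the trigger for a secondary outcome. Patients answer online, and the Patient Selection section says that submitted responses cannot be edited. A score placed under a mixed instruction therefore stays as given, and an analysis cannot recover what the patient meant.

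**Working it through.** No figure in the Protocol depends on this point, so the check is a comparison of the texts.

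**1. Explanation against diary**

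| Element | Postoperative Pain Assessment | Appendix 2 |
|---|---|---|
| Band labels | no, mild, moderate, severe | same |
| Cut-points | 0, 1–3, 4–6, 7–10 | same |
| Reference to analgesics in the bands | in mild, moderate and severe | none |
| Meaning of 10 | unbearable | worst possible |
| *Unbearable* also used for | all of 7–10 | not used |

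**2. What a patient can judge before a first dose**

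The severe descriptor has three elements: the pain is unbearable, analgesics do not control it adequately, and it often calls for rest. The first and third can be judged without taking anything. The second cannot. A patient who follows the advice has taken no ibuprofen before reaching severe pain, and the exclusion criteria rule out analgesic use in the 7 days before treatment.

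The moderate descriptor has the same gap. It says that analgesics can control the pain, in a band where the patient is advised not to take the prescribed one.

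**3. Pain of 8 that ibuprofen relieves**

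- By number: 8 lies in 7–10, so it is severe.
- By the analgesic wording: the pain was controlled, so it fits the moderate description (4–6).

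A patient guided by the wording would have to move the score down by at least 8 − 6 = 2 points. A lower score at a later time point because ibuprofen has worked is a different matter: that is a true reading of pain at that time.

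**4. How much of the scale is touched**

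- The scale has 11 scores (0 to 10).
- The severe descriptor covers 7, 8, 9 and 10: 4 of 11.
- The moderate descriptor that names analgesic response covers 4, 5 and 6: 3 of 11.
- *Unbearable* marks 1 score as the anchor (10) and 4 scores as the band (7–10).

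These counts show where the wording can act. They do not show how often it does.

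**5. Direction**

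All four groups get the same explanation, diary and analgesic advice, and patients are to be blinded. Nothing in the wording makes a given intensity of pain score differently in one group than in another.

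**The case against.** The strongest reply is that the form on which patients enter the score is already sound. It asks for intensity, uses plain labels and has the same cut-points, so a patient can identify severe pain as 7 or more whatever the explanation says. The phrase about analgesics can also be read as a general picture of bad pain, not as a test that study ibuprofen must first fail, and the other two elements need no dose. Both top anchors are extreme, and nothing in the Protocol shows that patients would score differently under them. This largely stands, and it is why the point is minor. It does not remove the conflict, because the Protocol commits to giving patients the analgesic wording as well as the form.

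Four stronger readings are tempting, and the Protocol does not support them.

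- *A reader might infer bias between groups.* The wording is common to all groups and patients are blinded, so there is no route to it.
- *A reader might infer that ibuprofen is forbidden below severe pain, or that the rule cannot be followed.* Patients are advised, not prohibited, and the numbers make the rule usable.
- *A reader might want to express the effect as a loss of power.* The Protocol gives no NRS variance and no frequency of scores near 6/7 or at the top. Random one-point noise spread over all scores would not represent the mechanism, which acts only near the moderate–severe boundary and at the top of the scale.
- *A reader might infer that the effect of ibuprofen on pain is lost to analysis.* The diary records the drug, the dose, the time taken and the time of each score. Only misplacement caused by the wording is beyond repair.

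**Conclusion.** The point holds as a minor inconsistency in patient-facing wording. The severe band is explained partly by analgesic failure, which a patient following the ibuprofen advice cannot judge before a first dose. One word, *unbearable*, serves for both 10 and the whole 7–10 band, and the diary gives 10 a different anchor.

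The likely consequence is a small, non-differential loss of precision in severe-range NRS scores and in ibuprofen use. Its size cannot be calculated from the Protocol. The judgement that it is small rests on the agreement of labels and cut-points and on the form being intensity-only. The judgement that it is non-differential rests on common wording and on the blinding of patients being kept. The consent pages are not in the copy reviewed, so any further wording given to patients could not be checked.

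**What to change.** Before patients receive the materials:

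1. Replace the band descriptions in Postoperative Pain Assessment with the diary's labels alone: no, mild, moderate and severe pain, with the existing cut-points.
2. Use one top anchor in both places. The diary's (10 as the worst possible pain) is the better choice, because *unbearable* is also used for the whole severe band.
3. State the ibuprofen advice as NRS 7 or more. This keeps the present rule and removes any need to judge analgesic response.

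The Protocol describes recruitment in the future tense but does not state whether enrolment has started. If it has, record the date of the change, so that scores given under the two wordings can be told apart.

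The cost is a minor edit to the Protocol and patient materials, with most of the wording taken from the diary. Visits, sample size and data items stay as they are.

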Appendix 2. Patient Pain Diary Form

Study Title: Impact of Trunatomy and Protaper Gold Ni-Ti Systems Using Resin-Based or Bioceramic Sealers on Postoperative Pain After Root Canal Treatment: A Randomized Clinical Trial

Participant ID: _____

Date of Treatment: _____

Tooth Number: _____

Instructions to the Patient

After your root canal treatment, please record the level of pain you experience at the following time intervals. Use the Numerical Rating Scale (NRS) below to indicate the intensity of your pain:

Pain Score	Description
0	No pain
1–3	Mild pain
4–6	Moderate pain
7–10	Severe pain

Numerical Rating Scale (NRS): 0 1 2 3 4 5 6 7 8 9 10
(0 = No Pain 10 = Worst Possible Pain)

Pain Record Table

Time After Treatment	Date / Time Recorded	Pain Score (0–10)	Notes (e.g., pain type, analgesic taken, other symptoms)
6 hours			
12 hours			
24 hours			
48 hours			
72 hours			
7th day			

Analgesic Use (if any):

Medication Name	Dose	Time Taken	Reason (if other than pain)

Patient Signature: _____ Date: _____

Investigator Signature: _____ Date: _____
